**23. Individuals With Impaired Decision-Making Capacity:**

Will participants potentially lacking capacity to provide informed consent be eligible to enroll in this study?  Yes  No

If yes, respond to **Research Involving Individuals With Impaired Decision-Making Capacity: Attachment G**

**24. Recruitment:**

**Describe how subjects will be recruited for participation in this study:**

Eligible participants may be identified from medical record information as a “preparatory to research” activity under the HIPAA Privacy Rule. Protected health information obtained as a preparatory to research activity may not be removed by a researcher from DHMC, including on mobile electronic storage devices. Contact with the identified participants, however, may not occur without prior D-HH approval of the recruitment plan for the study. This plan should describe how initial contact with participants will be made and by whom. Please note in general, individuals should not be contacted for recruitment into a research study by someone unknown to the individual.

a) Will subjects be recruited by searching records (e.g., school records, medical records)?

Yes  No

If yes, will this search include paper files?

Yes  No

If yes, where will these paper files be located?

If yes, will this search include electronic files?

Yes  No

If yes, who maintains these electronic files?

b) Will databases be utilized?

Yes  No

If yes, please specify types and locations of databases: **Patients will be recruited from the clinical**

**patient pool of patients of the Dartmouth Epilepsy Program. No specific or pre-existing database will be searched.**

c) Will fliers or brochures be posted, mailed or otherwise distributed?

Yes  No

d) Will letters be sent to potential participants?

Yes  No

If yes, please provide the letter(s) for D-HH review.

e) Will referral be utilized for recruitment?

Yes  No

If yes, please be aware patients should first be informed about the study and agree to the contact before any referral.

f) Will any other method be employed?

Yes  No

If yes, please specify, in detail, what those methods will be:

Patients who are candidates for intracranial EEG monitoring for presurgical evaluation of medically refractory epilepsy will be asked in the outpatient clinic or over the telephone by their clinician if they would like to participate in a clinical study. If they do, they (and their legal guardian, if applicable) will be provided with all pertinent study information.

g) Does the research plan include “finder fees” or incentives (bonus payment, gift certificates) offered to study personnel for enrollment of participants?

Yes  No

Note: As a rule, finder fees or incentives are not acceptable. Please justify any offered incentives. If incentives become available during the course of the study, please notify D-HH.

Attach copies of any proposed flyers, posters, pamphlets, print advertisements, and scripts for on-air advertisements or telephone calls. All recruitment materials should be approved by D-HH prior to use.

Note: Advertising should not use terms such as “new treatment,” “new medication,” or “new drug” without explaining that the test article is investigational. A phrase such as “receive new treatments” implies that research participants will be receiving newly marketed products of proven worth. Advertisements should not promise “free medical treatment,” when the intent is only to say participants will not be charged for taking part in the investigation. D-HH will determine if the promise of treatment without charge is an inappropriate inducement for study participation. Advertisements may state that participants will be paid, but should not emphasize the payment or the amount to be paid. The advertisement should include: the name and address of clinical investigator and research facility; the condition under study or the purpose of the research; in summary form, the criteria that will be used to determine eligibility for the study; a brief list of participation benefits, if any (e.g., a no-cost health examination); the time or other commitment required of the participants; and the location of the research activities; and the person or office from whom to obtain further information.

## **25. Consent Process:**

The Principal Investigator (PI) is responsible for ensuring all participants have provided informed consent to participate in this study unless the consent process is waived or altered by D-HH. The PI may authorize other appropriately trained individuals to obtain consent from participants.

Please file the consent form in the medical record of each research participant if study participation may affect other medical treatment.

Explain how informed consent to research participation will be obtained. Please describe the consent process, including information about:

- Who has been authorized by the PI to obtain consent
- The time interval between providing information potential participants about a study and having the consent form signed
- Any precautions taken to minimize the possibility of coercion or undue influence

- Plans for responding to a potential participant or a legally authorized representative who does not speak English, such as the use of a translator or a translated consent form
- Any aids used to simplify scientific or technical information, like a diagram
- Plans to accommodate the probable literacy level of potential participants

[name] or a qualified, appropriately trained person designated by [name] will be responsible for the consent process. All persons designated by [name] to obtain consent will have completed the Protection of Human Subjects training, or the equivalent accepted by D-HH. The patients will be seen in the outpatient epilepsy clinic to discuss intracranial EEG monitoring prior to epilepsy surgery. The consent will take place at the same clinic visit. Patients who do not have a clinic visit scheduled prior to admission (usually due to travel distance) will be contacted by their clinicial via telephone. If they are interested, a consent form will be sent to them for review, and their signature obtained on the day of their admission. Undue coercion will be minimized by the team approach to determining who is a candidate for intracranial EEG study. That is, the decision for iEEG and implant plan is made during epilepsy surgery conference and requires the unanimous approval of all involved physicians. Only patients who require iEEG will be approach to participate in the study. We will not obtain research testing on patient who cannot understand or speak English. We may show patients actual examples of the electrodes used for routine clinical care and the dual electrodes to help them make the decision.

Patients who are not able to provide informed consent will be considered for participation in the study if: 1) they meet the inclusion criteria; 2) they are interested in participating in the study and; 3) in the judgement of the research team they are capable of performing the cognitive tasks. In those instances the patient and their legal guardian will both participate in the informed consent process, with the legal guardian signing the consent form.

I intend to obtain consent for research participation but I am requesting a waiver for the use of a *signed and dated* consent form. Please respond to the criteria listed in **Attachment I** and include an information sheet based on the D-HH template.

I am requesting an alteration of the consent process to exclude certain information that is ordinarily required. A list of the essential elements of consent to research participation is available on the CPHS website: <http://www.dartmouth.edu/~cphs/tosubmit/ConsentElements.html>.

Please respond to **Attachment H**.

I am requesting a waiver of the entire consent process and use of a consent form. Please respond to **Attachment H**.

Explain why any alteration or waiver to the consent process or form is necessary.

**b) Authorization:** Explain how an authorization for research use of protected health information (PHI) will be obtained. PHI is individually identifiable health information obtained from a health care provider or insurance plan. In general, the HIPAA Privacy Rule permits the use or disclosure of PHI for research purposes only with an authorization from each participant whose PHI will be involved. Only when certain criteria are satisfied can D-HH grant a waiver of authorization or of the use of a signed and dated authorization form. A waiver of authorization is necessary for recruitment procedures when patient information is used to identify and contact potentially eligible research participants. A single

form may combine the essential information for both consent and an authorization. The D-HH consent template contains this combination and is available on the [D-HH](#) website.

*Check all that apply:*

- This study does not involve PHI.
- A single form combining an authorization with the consent form and based on the CPHS template is included with this application.
- A separate authorization form is included with this application.
- I am requesting a waiver of authorization for only the recruitment procedure. Please respond to **Attachment H**.
- I am requesting a waiver of *signed and dated* authorization. Please respond to **Attachment I**.
- I am requesting a waiver of authorization for the use or disclosure of PHI in this entire study. Please respond to **Attachment H**.

In your explanation of the consent process above, please include information about obtaining authorization for the research use of PHI.

## **26. Privacy and Confidentiality:**

Describe the plans to protect the privacy of subjects and maintain the confidentiality of the data.

Note: Under certain circumstances, an invasion of privacy or breach of confidentiality may present a risk of serious harm to subjects (e.g., as when the research obtains information about subjects that would, if disclosed by the researcher, jeopardize jobs or lead to prosecution for criminal behavior). Under other circumstances, an invasion of privacy or breach of confidentiality can be a moral wrong

**a)** Will any study activities involve an interaction or reveal information for which protection of participant privacy is necessary?

- Yes
- No

If yes, please identify the activities and describe the plan to protect the privacy of participants. For example, a plan for protection of privacy might consist of conducting the assent process for an adolescent minor in a private setting, rather than in the presence of the minor's parent.

Data recorded during the study will include the names of patients, their dates of birth, medical record numbers, and results of testing. This information will be kept on DHMC servers. Data sent from DHMC to collaborators at Columbia University will be de-identified. Access to the data will only be available for investigators involved in the study.

De-identified EEG data collected for this study will be shared with other academic institutions, and added to public databases of EEG data. Data shared in this way will not include any identifying information.

**b)** Will the data collected in the course of the study be considered sensitive, e.g., include information about a mental health disorder, HIV status, or SS#?

- Yes
- No

If yes, provide the rationale for why these data are needed:

If yes, could any of these data, if disclosed, damage financial standing, employability, insurability, or reputation?

Yes  No

If yes, will a Certificate of Confidentiality be obtained?

Yes  No

Any person engaged in research collecting information about illegal conduct from human research subjects may apply for a Certificate of Confidentiality. NIH provides detailed instructions for investigators wishing to make an application at <http://grants.nih.gov/grants/policy/coc/index.htm>.

**c)** Describe specific physical, administrative, and technical safeguards employed to protect confidentiality of data, e.g., coding with the removal of identifiers, limitation of access to data, use of locked file cabinets, protection of computer-based data systems.

Sensitive patient information will be stored on DHMC servers.

**d)** Will data that identify individual subjects be published or in any way be disclosed to third parties other than project personnel?

Yes  No

If yes, please explain here and incorporate the information in consent form:

(This section is empty)

**27. Responsibility for costs of injury or illness related to research:**

Will the sponsor or other funding agency be responsible for costs of injury or illness related to the research?

Yes  No

If applicable, describe whether or not the sponsor will be responsible for investigational device removal if required:

Use of microelectrodes is generally considered safe. A single retrospective analysis of the use of the dual macro-micro electrode system has shown no significant complications above that for the use of macroelectrodes. Specific macroelectrode complications do occur. If any complications such as infection or hemorrhage occur, they will be attributable to the macroelectrode part, and not the microelectrode. Therefore, the cost of complications should be covered by the health insurance plan as these would be expected to occur in standard electrode patients.

**If the sponsor or other funding agency will not be responsible for costs of injury or illness related to research, please complete:**

**a)** The reasons why the sponsor or funding agency is not accepting responsibility for research-related injury.

We anticipate that any complications will be related to the implant or admission generally, and not specific to the research portion of the electrodes or the study tasks.

**b)** Summary of risks as related to potential costs that could be incurred as a result of research-related injury or illness.

**c)** Describe reasons for requesting that DHMC or Dartmouth College provide coverage for research-related injury or illness, which is not standard policy.

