Epilepsy Center on hundreds of patients since 1992. The recording of iEEG for conventional clinical applications is done using a standard macroelectrode system. A macroelectrode is either a soft plastic strip with multiple 5 mm disc electrodes or a rigid 10 cm needle electrode with multiple contacts along its length. Macroelectrodes are designed to record the summated activity of relatively large groups of neurons located in the vicinity of the electrode contact. Although macroelectrode iEEG recording is the mainstay of surgical epilepsy with established clinical indications, significant limitations are known.

Currently, several well-established epilepsy centers in the United States (for instance, UCLA and Mayo Clinic) are investigating the use of microelectrode systems in epilepsy surgery to supplement the standard macroelectrode recording. Microelectrodes are ultra thin filament electrodes with tip diameters of 3 to 10 micrometers which are able to record the activity of small groups or even single neurons, i.e. single unit potential recording. Supplementary microelectrode recordings are obtained using commercially available, FDA-approved, dual macro-micro electrode systems. These dual systems do not require the insertion of separate and additional microelectrode catheters but use the standard iEEG electrode to deliver the microelectrodes to the target brain regions. The major benefit of this novel design is that the rate of complications from such dual electrode systems is the same and for the standard iEEG electrodes.

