#### **8.Data and Safety Monitoring:**

Describe plans for data and safety monitoring to ensure the safety of subjects and the quality of the data. As described in federal guidance "... a variety of types of monitoring may be anticipated depending on the nature, size, and complexity of the trial. In many cases, the principal investigator would be expected to perform the monitoring function." This plan should include monitoring to determine:

The progress of the trial, including periodic assessments of data quality and timeliness, participant recruitment, accrual and retention, participant risk versus benefit, and other factors that can affect study outcome. Monitoring should also consider factors external to the study when interpreting the data, such as scientific or therapeutic developments that may have an impact on the safety of the participants or the ethics of the study.

Note: This section does not request information related to sponsor study monitor visits. This section requires a description of an adequate data and safety monitoring plan.

The safety of dual macro-micro electrodes will be assessed with every patient. Complete data analysis will be done with every patient.

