The risk of participation in the study overall is only minimally greater than standard iEEG recording, although conclusive risk assessment is not available. The safety of dual micro-macro electrode systems has been analyzed in a retrospective study done at the Mayo Clinic by Van Gompell et al. In this study, 24 consecutive patients underwent long-term iEEG monitoring with implanted dual depth and subdural grid and strip electrodes; both clinical macroelectrodes and research microelectrodes were used. The patients included 18 women and 6 men with an average age of 35 (range 21–65). The mean hospital stay was 11 days (range 5–20), with mean duration of implantation 7.0 days (range 3–15). Data from the 198 consecutive craniotomies for standard clinical subdural grid insertion (prior to surgery in the 24 patients described here) were used for comparison to investigate the relative risk of complications. The overall complication rate was 4.2% (only 1 patient had a complication), which did not significantly differ from the complication rate previously reported by the authors of 6.6% when standard subdural and depth intracranial electrodes were used. There were no deaths or permanent neurological deficits related to electrode implantation. In conclusion, the authors demonstrated the use of hybrid subdural strip and grid electrodes containing standard clinical macroelectrodes. In this initial study in 24 patients, the complication rate is acceptable, and there does not appear to be increased risk associated with the use of hybrid electrodes compared with standard subdural and depth iEEG electrodes. Please refer to Attachments #1 and #2 for further details.

Digital Lynx system is not FDA approved. However, it has been certified to be UL/EN 60601-1 and 60601-22 compliant. Details are enclosed in attachment #3.

A theoretical risk of potential physical neuronal injury by direct contact of a microelectrode with a neuron exists. This type of injury has not been reported in humans with use of microelectrodes. Potential injury by direct microelectrode contact would most likely be limited to single neurons or very small populations of neurons. No neurocognitive effect would be expected by injury to such small populations of neurons.

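### One complication in 24 patients does not support calling the dual-electrode complication rate the same as standard, and section 27 assigns any infection or hemorrhage to the macroelectrode before it occurs

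*Combined protocol and SAP*

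**What the plan says.** The plan describes the risk of the dual macro-micro electrodes in several places.

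- **Section 3 (Introduction)** argues that no separate catheter is needed and concludes, without a hedge, that "the rate of complications from such dual electrode systems is the same and for the standard iEEG electrodes".
- **Section 13 (Risks), item b:** "The risk of participation in the study overall is only minimally greater than standard iEEG recording, although conclusive risk assessment is not available". The evidence is one retrospective series of 24 patients: "The overall complication rate was 4.2% (only 1 patient had a complication"). The plan reports no significant difference from the 6.6% that the same authors had found earlier with standard electrodes.
- **Attachment G, item b** says that, to the best of the team's knowledge, implanting electrodes with micro contacts carries no more risk than implanting standard ones.
- **Section 17, item b** relies on minimal risk to add no protection beyond guardian involvement for people with a cognitive disability.
- **Section 27** says that the retrospective analysis "has shown no significant complications above that for the use of macroelectrodes". It then says "If any complications such as infection or hemorrhage occur, they will be attributable to the macroelectrode part, and not the microelectrode", and concludes that the health plan should bear the cost. Item a is softer: "We anticipate that any complications will be related to the implant or admission generally, and not specific to the research portion of the electrodes".
- **Section 8 (Data and Safety Monitoring)** says "The safety of dual macro-micro electrodes will be assessed with every patient". It describes no procedure for judging causality.

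**The concern.** Two statements go further than the plan's own evidence.

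The first is equality of risk. A comparison based on one event can be non-significant whether the true rates are equal or quite different, so it cannot carry an unhedged claim that they are equal.

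The second is attribution. The micro part is the research component; section 6 has it bought with research funds. Section 27 decides before any patient is implanted that an infection or hemorrhage belongs to the other part. Applied as written, that sentence would stop any such event from being treated as related to the research component, and the per-patient safety assessment in section 8 could not detect a problem of that kind.

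The risk wording also bears on a decision. Attachment G bars people who lack capacity from a study that offers little chance of direct benefit and involves a meaningful increase in risk. Item a of that attachment concedes that direct benefit is unlikely, so the answer on risk matters. The IRB reads there that implant risk is no higher, while section 13 says that overall risk is slightly higher and not conclusively assessed.

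**Working it through.** **Inputs.** Dual electrodes: 1 complication in 24 patients (section 13). Comparator: 6.6% with standard electrodes (section 13), treated as a fixed reference. Confidence level: two-sided 95%, my assumption, since the plan sets none for safety.

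**Step 1, the plan's own figure.** 1/24 = 0.0417, or 4.2%. It reproduces.

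**Step 2, precision.** Exact (Clopper-Pearson) limits:

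- Lower: 1 − 0.975^(1/24) = 0.00105, or 0.1%.
- Upper: the p that solves (1 − p)^24 + 24p(1 − p)^23 = 0.025, which is 0.2112, or 21.1%.
- Upper limit over comparator: 21.12 / 6.6 = 3.2.

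**Step 3, what a series of 24 can show.** P(0 or 1 event) = (1 − p)^24 + 24p(1 − p)^23. The doubling and tripling are my illustrations; the plan states no margin.

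| True rate | Expected events in 24 | P(0 or 1 event) |
|---|---|---|
| 6.6% (comparator) | 24 × 0.066 = 1.58 | 52.4% |
| 13.2% (doubled) | 24 × 0.132 = 3.17 | 0.0335 + 0.1221 = 15.6% |
| 19.8% (tripled) | 24 × 0.198 = 4.75 | 3.5% |

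A result as low as the one observed is unremarkable at a doubled rate. It would be unusual at a tripled rate, although 19.8% still lies inside the interval.

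**Step 4, two-sample check, on an assumption.** Section 13 mentions 198 earlier craniotomies as the comparison series but does not say that 198 is the denominator of the 6.6%. If it is, the count must be 13 (13/198 = 6.57%; 12 gives 6.06% and 14 gives 7.07%). Then:

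- Fisher exact p = 1.0, so the reported non-significance reproduces.
- Relative risk = (1/24)/(13/198) = 0.63, 95% CI 0.09 to 4.64.
- Difference = −2.4 percentage points, 95% CI −7.9 to +13.9.
- Exact power to detect a doubling to 13.2% is about 20%.

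The comparison had little chance of finding a doubling.

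**Step 5, attribution.** This needs no arithmetic. The visible text does not say what the one complication was or which part of the electrode was held responsible. Section 13 names a theoretical hazard specific to the microelectrode (contact injury to neurons). Section 3 says that the standard electrode delivers the microelectrodes, so the two parts may not be separable for a given event. None of this supports a rule that infection or hemorrhage always belongs to the macro part.

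**The case against.** The strongest reply has four parts.

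1. **Scope.** Section 3 speaks of the complication rate and argues from design, Attachment G of implanting, and section 13 of participation overall, including a recorder that is not FDA approved. A reader might infer that the three statements flatly contradict each other. They do not: implant risk could be no higher while overall risk is slightly higher. This stands, and it is why the point rests on the evidence behind the wording. The design argument makes a similar rate plausible, but it is not rate data.
2. **Disclosure.** Sections 4 and 13 state that the evidence is a single retrospective study of 24 patients, section 13 gives the event count and says conclusive assessment is not available, and Attachment G is hedged. This also stands. Nothing is concealed; what is missing is the interval, and a section 3 statement that matches it.
3. **Section 27 is about cost.** Item a is worded as an expectation, and section 8 does not adopt the attribution. A reader might infer that the plan will misclassify adverse events. No visible text says so. The sentence is nevertheless categorical, and section 8 has no procedure to set against it.
4. **No decision is shown to change.** A reader might infer that the Attachment G bar applies. The documents do not support that: the test is a meaningful increase, which the data neither show nor exclude, and guardian participation and signature are already provided in sections 17 and 25.

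**Conclusion.** Wrong as written, with minor to moderate severity. The series is compatible with a dual-electrode complication rate anywhere from 0.1% to 21.1%, so a doubling of 6.6% is not excluded. That does not support the unhedged equality in section 3 and gives only weak support to the hedged statement in Attachment G. No data in the text support the categorical attribution in section 27.

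A reader might infer that dual electrodes are riskier. The documents do not show that: the point estimate (4.2%) is below the comparator (6.6%), and the finding concerns imprecision only.

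The conclusion assumes a 95% level and takes 6.6% as a fixed reference; the two-sample figures also assume 13/198. It is limited to the visible text. Attachments #1 and #2, which the plan says address electrode safety, were not available and may hold further data. The tick for overall risk classification in section 13, item a, cannot be read.

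**What to change.** **Section 27.** Delete the categorical attribution, or reword it as an expectation about cost coverage that does not determine how events are classified.

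**Section 8.** Record each complication in a participant with a dual electrode, together with the electrode system used. Assess its relation to the macro part, the micro part or the implant procedure case by case, with a category for cases that cannot be determined.

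**Sections 3 and 13 and Attachment G, item b.** Use one risk statement, for example: *one complication in 24 patients (4.2%, exact 95% CI 0.1% to 21.1%), not significantly different from a historical 6.6%, but an increase over standard electrodes cannot be excluded.* Refer to it in section 17, where minimal risk is the reason for adding no further protections.

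**Cost.** Wording changes and a short causality entry for each complication, with no added visits or procedures. The safety figure will read less favourably, the cost rationale in section 27 must stand without the attribution, and the IRB may need to look again at Attachment G.
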